4.6 WEAR AND REPLACEMENT SCHEDULES, INCLUDING FORM, PACKAGING AND LABELING

Wear Schedule: In addition to the trial fitting at the first visit, the study lenses will be worn for a period of approximately three to four hours while attending the study measurement visits.

Replacement Schedule: The study lenses will only be worn once and disposed of after use.

Test Article Packaging Description: Single vials.

Labeling: The study contact lenses are CE marked and marketed in the UK and will carry the approved CE marking.

4.7 DETAILED STUDY PROCEDURES

4.7.1 SEQUENCE OF EVENTS

Visit 1: Enrolment / Fitting			
Step	Descriptor	Details	Reference Document
1.	Statement of Informed Consent	Each subject must read, understand and sign the Statement of Informed Consent before being enrolled in the study. A witness must also sign the form. Note: The subject must be provided with a signed copy of this document.	
2.	Demographics	Age, gender, race, and ethnicity,	
3.	Medical History	Questions regarding the subjects' medical history.	
4.	Concomitant Medications/ Treatments	Questions regarding the subjects' medications and/or treatments.	
5.	Contact Lens History	Questions regarding the subjects' habitual contact lenses and wearing patterns.	
6.	Subject Reported Ocular Symptoms	Record any symptoms or problems that the subject may experience with their habitual contact lenses, if applicable. Subject will not be asked about specific categories of complaints, but the severity or frequency will be recorded in the following categories: 
 • Burning/Stinging • Itchiness/Scratchiness • Dryness • Lens Awareness • Grittiness/Foreign Body Sensation • Redness • Irritation/Discomfort • Cloudy/Blurry/Hazy • Variable Vision • Other 	
7.	Distance Spherocylindrical Refraction and Entrance Visual Acuity	An optimal, binocular balanced distance spherocylindrical refraction will be performed. The distance visual acuity to the nearest letter will be recorded OD, OS and OU. Note: Best distance visual acuity with spherocylindrical refraction must be at least 20/30 in each eye for the subject to enroll in the study.	Manual of Procedures [REDACTED]
8.	Best Sphere Refraction	An optimal, distance best sphere refraction will be performed. The distance visual acuity to the nearest letter will be recorded.	Manual of Procedures [REDACTED]

9.	Ocular Dominance	The distance ocular dominance will be determined with the best distance correction in place using the +1.00 blur test. If the results are equivocal the sighting dominance test will be used to determine the dominant eye for the study.	Manual of Procedures
10.	Keratometry	Keratometry readings will be taken for each eye using an Autokeratometer. Steep and Flat K readings will be recorded in mm and axis.	Manual of Procedures
11.	Pupil size measurement	The measurements will be carried out at three luminance: 250, 50 and 2.5 cd/m ²	Manual of Procedures
12.	HVID measurement	Horizontal visible iris diameter will be recorded in millimeters with one decimal place.	Manual of Procedures
13.	Biomicroscopy	Biomicroscopy will be performed OD and OS. Standard Slit Lamp Classification Scales will be used to grade the findings. For the limbal and conjunctival redness, 0.5 unit increments will be used in the grading.	Manual of Procedures [REDACTED]
14.	Eligibility	All responses to Inclusion Criteria questions must be answered “yes,” and all responses to Exclusion Criteria questions must be answered “no” for the subject to be considered eligible.	
15.	Lens Information	The initial contact lenses will be selected based upon the fitting guide. Place the lenses on the subject’s eyes.	Appendix B
16.	Lens Damage	Inspect the lenses on eye with the biomicroscope for damage and if damaged, record the damage and have the subject insert a new lens. Save worn, damaged lenses in sterile saline in the labeled vials provided with the study materials and complete the quality product complaint form.	
17.	Lens Settling	Allow the lenses to settle for at least 15 minutes.	
18.	Spherical Over-Refraction and Visual Acuity	A monocular distance spherical over-refraction will be performed. The distance visual acuity to the nearest letter will be recorded OD, OS and OU.	Manual of Procedures [REDACTED]
19.	Subjective Lens Fit Assessment	Lens centration, primary gaze movement, upgaze movement and tightness (push-up test) will be evaluated and graded. The subject should not proceed to wear the contact lenses if any of the following is observed: 
 • presence of limbal exposure (appearance of clear cornea) in any gaze • presence of edge lift • presence of unacceptable movement (excessive or insufficient) in all three 	Manual of Procedures [REDACTED]

		movement categories (primary gaze, upgaze, and push-up).	
20.	Modifications	If the subjects vision is or the Investigator determines that the visual acuity or over-refraction are not acceptable then a lens modification must be made (Repeat Steps 15 to 19). The fitting guide must be followed, allowing for at least 10 minutes settling time between lens changes.	
21.	Final lens parameters	Based on Lens Fit Evaluations, final lens parameters will be recorded.	
22.	Familiarization with visual performance assessment tasks	The subject will undergo familiarization with the study visual performance assessment tasks (time controlled visual acuity, detection tests, driving simulation and computer based reaction time game).	Manual of Procedures
23.	Lens Removal	The contact lenses are removed and discarded.	
24.	Biomicroscopy	Biomicroscopy will be performed OD and OS. Standard Slit Lamp Classification Scales will be used to grade the findings. For the limbal and conjunctival redness, 0.5 unit increments will be used in the grading.	Manual of Procedures [REDACTED]
25.	Distance Spherocylindrical Refraction and Exit Visual Acuity	An optimal, binocular balanced distance spherocylindrical refraction will be performed. The distance visual acuity to the nearest letter will be recorded OD, OS and OU.	Manual of Procedures [REDACTED]
26.	Continuance	Indicate whether the subject will continue to the next visit. If not, proceed to Final Evaluation.	
27.	Lens Order	Custom Test and Control lenses will be ordered. Visit 2 will be scheduled once the study lenses are received.	

Visit 2: First Measurement Visit (2 to 6 weeks after Visit 1)			
Step	Descriptor	Details	Appendix
1.	Concomitant Medications/Treatments	Questions regarding the subjects' medications and/or treatments.	
2.	Subject Reported Ocular Symptoms	Record any symptoms or problems that the subject may experience with their habitual contact lenses, if applicable. Subject will not be asked about specific categories of complaints, but the severity or frequency will be recorded in the following categories: 
 Burning/Stinging Itchiness/Scratchiness 	[REDACTED]

		
 • Dryness • Lens Awareness • Grittiness/Foreign Body Sensation • Redness • Irritation/Discomfort • Cloudy/Blurry/Hazy • Variable Vision • Other 	
3.	Distance Spherocylindrical Refraction and Entrance Visual Acuity	An optimal, binocular balanced distance spherocylindrical refraction will be performed. The distance visual acuity to the nearest letter will be recorded OD, OS and OU.	Manual of Procedures [REDACTED]
4.	Biomicroscopy	Biomicroscopy will be performed OD and OS. Standard Slit Lamp Classification Scales will be used to grade the findings. For the limbal and conjunctival redness, 0.5 unit increments will be used in the grading.	Manual of Procedures [REDACTED]
5.	Continuance	Indicate whether the visit needs to be rescheduled.	
6.	Randomization	Study Lens Type will be selected based on the Randomization Scheme	
7.	Study lens insertion	The initial study contact lenses will be selected based upon the randomization schedule. Place the lenses on the subject eyes.	
8.	Lens Damage	Inspect the lenses on eye with the biomicroscope for damage and if damaged, record the damage and have the subject insert a new lens. Save worn, damaged lenses in sterile saline in the labeled vials provided with the study materials and complete the quality product complaint form.	
9.	Lens Settling	Allow the lenses to settle for at least 15 minutes.	
10.	Spherical Over-Refraction and Visual Acuity	A monocular distance spherical over-refraction will be performed. The distance visual acuity to the nearest letter will be recorded OD, OS and OU.	Manual of Procedures [REDACTED]
11.	Subjective Lens Fit Assessment	
Lens centration, primary gaze movement, upgaze movement and tightness (push-up test) will be evaluated and graded.
 
The subject should not proceed to wear the contact lenses if any of the following is observed:
 
 • presence of limbal exposure (appearance of clear cornea) in any gaze • presence of edge lift • presence of unacceptable movement (excessive or insufficient) in all three movement categories (primary gaze, upgaze, and push-up). 
If either lens is deemed unacceptable, the
	Manual of Procedures [REDACTED]

		subject will be discontinued from the study. Remove the lenses, perform a slit-lamp evaluation, and complete the Final Evaluation form.	
12.	Visual Field Measurement	Esterman visual fields will be measured OD, OS and OU using a Humphrey perimeter.	Manual of Procedures
13.	Vision Assessments	
Time Controlled Visual Acuity (TCVA) Measurements will be made at 4m using 2.5 and 250 cd/m² luminance, and at 67cm using 50 cd/m² luminance. The luminance requirements will be the same at the target and at the eye. Monocular and binocular visual performance will be measured for the following conditions:
 
 • Distance 2.5 cd/m² 
 ○ Central ○ 5 degrees eccentricity ○ 20 degrees eccentricity • Distance 250 cd/m² 
 ○ Central • Intermediate 50 cd/m² 
 ○ Central ○ 5 degrees eccentricity ○ 10 degrees eccentricity 
The order of luminances tested will be randomized.
 
Subjects will undergo a driving simulation test and subsequently make a subjective assessment of their visual performance.
 
Subjects will play computer based reaction time games and subsequently make a subjective assessment of their visual performance.
	Manual of Procedures
14.	Lens Removal	The contact lenses are removed and discarded.	

15.	Biomicroscopy	
Biomicroscopy will be performed OD and OS. Standard Slit Lamp Classification Scales will be used to grade the findings. For the limbal and conjunctival redness, 0.5 unit increments will be used in the grading.
	
Manual of Procedures
 
16.	Distance Spherocylindrical Refraction and Exit Visual Acuity	An optimal, binocular balanced distance spherocylindrical refraction will be performed. The distance visual acuity to the nearest letter will be recorded OD, OS and OU.	
Manual of Procedures
 
17.	Continuance	Indicate whether the subject will continue to the next visit. If not, proceed to Final Evaluation.	

Visit 3: Second Measurement Visit (2 to 14 days after Visit 2)			
Step	Descriptor	Details	Appendix
1.	Concomitant Medications/Treatments	Questions regarding the subjects' medications and/or treatments.	
2.	Subject Reported Ocular Symptoms	Record any symptoms or problems that the subject may experience with their habitual contact lenses, if applicable. Subject will not be asked about specific categories of complaints, but the severity or frequency will be recorded in the following categories: 
 • Burning/Stinging • Itchiness/Scratchiness • Dryness • Lens Awareness • Grittiness/Foreign Body Sensation • Redness • Irritation/Discomfort • Cloudy/Blurry/Hazy • Variable Vision • Other 	
3.	Distance Sphero-cylindrical Refraction and Entrance Visual Acuity	An optimal, binocular balanced distance sphero-cylindrical refraction will be performed. The distance visual acuity to the nearest letter will be recorded OD, OS and OU.	Manual of Procedures
4.	Biomicroscopy	Biomicroscopy will be performed OD and OS. Standard Slit Lamp Classification Scales will be used to grade the findings. For the limbal and conjunctival redness, 0.5 unit increments will be used in the grading.	Manual of Procedures
5.	Continuance	Indicate whether the visit needs to be rescheduled.	
6.	Randomization	Study Lens Type will be selected based on the Randomization Scheme	
7.	Study lens insertion	The initial study contact lenses will be selected based upon the randomization schedule. Place the lenses on the subject eyes.	
8.	Lens Damage	Inspect the lenses on eye with the biomicroscope for damage and if damaged, record the damage and have the subject insert a new lens. Save worn, damaged lenses in sterile saline in the labeled vials provided with the study materials and complete the quality product complaint form.	
9.	Lens Settling	Allow the lenses to settle for at least 15 minutes.	
10.	Spherical Over-Refraction and Visual Acuity	A monocular distance spherical over-refraction will be performed. The distance visual acuity to the nearest letter will be recorded OD, OS and OU.	Manual of Procedures

11.	Subjective Lens Fit Assessment	
Lens centration, primary gaze movement, upgaze movement and tightness (push-up test) will be evaluated and graded.
 
The subject should not proceed to wear the contact lenses if any of the following is observed:
 
 • presence of limbal exposure (appearance of clear cornea) in any gaze • presence of edge lift • presence of unacceptable movement (excessive or insufficient) in all three movement categories (primary gaze, upgaze, and push-up). 
If either lens is deemed unacceptable, the subject will be discontinued from the study. Remove the lenses, perform a slit-lamp evaluation, and complete the Final Evaluation form.
	Manual of Procedures [REDACTED]
12.	Visual Field Measurement	Esterman visual fields will be measured OD, OS and OU using a Humphrey perimeter.	Manual of Procedures
13.	Vision Assessments	
Time Controlled Visual Acuity (TCVA) Measurements will be made at 4m using 2.5 and 250 cd/m² luminance, and at 67cm using 50 cd/m² luminance. The luminance requirements will be the same at the target and at the eye. Monocular and binocular visual performance will be measured for the following conditions:
 
 • Distance 2.5 cd/m² 
 ○ Central ○ 5 degrees eccentricity ○ 20 degrees eccentricity • Distance 250 cd/m² 
 ○ Central • Intermediate 50 cd/m² 
 ○ Central ○ 5 degrees eccentricity ○ 10 degrees eccentricity 
The order of luminances tested will be randomized.
 
Subjects will undergo a driving simulation test and subsequently make a subjective assessment of their visual performance.
 
Subjects will play computer based reaction time games and subsequently make a subjective assessment of their visual performance.
	Manual of Procedures
14.	Lens Removal	The contact lenses are removed and discarded.	

Final Evaluation			
Step	Descriptor	Details	Appendix
1.	Biomicroscopy	Biomicroscopy will be performed OD and OS. Standard Slit Lamp Classification Scales will be used to grade the findings. For the limbal and conjunctival redness, 0.5 unit increments will be used in the grading.	Manual of Procedures [REDACTED]
2.	Distance Spherocylindrical Refraction and Exit Visual Acuity	An optimal, binocular balanced distance spherocylindrical refraction will be performed. The distance visual acuity to the nearest letter will be recorded OD, OS and OU.	Manual of Procedures [REDACTED]
3.	Final Evaluation Form	Indicate the subject completed the study successfully or not. For subjects who discontinue, indicate the reason.	

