1.8 PROTOCOL SYNOPSIS

Protocol Number and Title: CR-5856 Evaluation Of The Effects Of a Black Annulus Within a Hydrogel Contact Lens on Visual Performance
Sponsor: JJVCI, [name]
Test Articles: Custom made CE marked commercially available hydrogel contact lenses with 1mm wide black annulus and 6mm inner diameter made from methafilcon A material by No7 Contact Lenses (Test). CE marked hydrogel contact lenses made from methafilcon A material by No7 Contact Lenses (Control). The design of the control contact lens is identical to the test contact lens, except that the test lens has the black annular ring.
Regimen and Dosing: At the fitting visit (Visit 1), up to two pairs of Fitting lenses will be trialed for approximately 20 to 30 minutes each for the purposes of determining the optimum study lens parameters and familiarization with the study procedures. Subjects will wear 2 of 2 study contact lenses (Test/Control or Control/Test per the randomization scheme) for a wearing time of approximately three to four hours at each of the two measurement visits (Visits 2 and 3), with the subjects remaining at the clinical site for the duration of the visits.
Phase or Type of Study: Pilot Study

Primary Objective:

The primary objective of the study will be to measure the binocular functional visual performance of the test and control contact lenses under distance day time conditions (250 cd/m²) for centrally presented high contrast (HC) time controlled visual acuity (TCVA) targets.

Secondary Objective:

The secondary objectives of the study will be to measure the binocular functional visual performance of the test and control contact lenses for the following conditions:

- i. Distance night time conditions (2.5 cd/m²) for centrally presented HC TCVA targets;
- ii. Intermediate vision indoor conditions (50cd/m²) for centrally presented HC TCVA targets.

Additional Measurements:

In addition to the primary and secondary objectives, the following will be measured:

- i. Monocular functional visual performance for centrally presented high contrast (HC) time controlled visual acuity (TCVA) targets.
 - a. Distance day time conditions (250 cd/m²)
 - b. Distance night time conditions (2.5 cd/m²)
 - c. Intermediate vision indoor conditions (50cd/m²)

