4.5 RANDOMIZATION AND MASKING

The lenses will not be dispensed and will be worn in a bilateral and random fashion using a 2x2 cross-over design. Permuted block randomization will be used to minimize the potential for treatment imbalance. A block size of two (2) will be utilized. A computer-generated randomization scheme will be provided by the study biostatistician to randomly assign subjects to one of two possible lens wear sequences (Test/Control or Control/Test) in a 1:1 manner. The order of applied distance as well as luminance within distance (if applicable) during vision assessments will also be randomized for each subject within lens type. The same orders applied for the first lens type will be used for the second lens type.

The random scheme will be generated using the PROC PLAN procedure from SAS Software Version 9.4 or higher (SAS Institute, Cary, NC).

The study site must follow the randomization scheme provided and complete the enrollment according to the randomization list and not pre-select or assign subjects. The randomized assignment of subjects will be performed at the beginning of Visit 2. The following must have occurred prior to randomization:

- Informed consent has been obtained
- Subject meets all the inclusion / exclusion criteria
- Subject history and baseline information has been collected

This is a subject-masked study. Study participants will be masked with respect to the sequence of study lens wear to which they have been assigned. An unmasked investigator will insert and remove the study lenses so that the subject is not aware of the study lens type. The identity of the study lenses will be unmasked to the investigator who will record the lens fitting measurements. However, the identity of the study lenses will be masked to the investigator who will collect measurements for the study primary and secondary endpoints.

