4.10 PROCEDURES FOR MAINTAINING AND BREAKING RANDOMIZATION CODES

Subjects who have had their lens assignment unmasked are expected to return for all remaining scheduled evaluations. A replacement subject may be enrolled if a subject discontinues from the study prematurely (see section 5.1); the decision whether to enroll replacement subjects will be made by the joint agreement of the Investigator and Sponsor.

When dispensing test articles, the following steps should be followed to maintain randomization codes :

1. Investigator or designee (documented on the Delegation Log) will consult the randomization scheme to obtain the study test article assignment for that subject prior to dispensing.
2. Investigator or designee will record the subject's number on the appropriate line of the randomization scheme.
3. Investigator or designee will pull the appropriate test articles from the study supply. All test articles that were opened, whether dispensed or not, must be recorded on the Test Article Accountability Log in the "Dispensed" section.

There will be an un-masked investigator at the site, therefore no provision is required for breaking randomization codes.

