9.7 EVALUABLE SUBJECTS

Accountability (disposition) of all enrolled subjects will be presented in each of the following status subgroups.

1. Completed: Randomized subjects who are eligible to participate in the study and have successfully completed all required visits including the final visit.
2. Discontinued: Randomized subjects who are prematurely discontinued from the study due to (i) lost to follow-up, (ii) withdrawal of consent, (iii) death, (iv) unsuccessful dispensing (lack of efficacy or safety), (v) safety reasons at the discretion of the investigator, (vi) dissatisfactory of eligibility criteria (e.g., pregnancy), (vii) noncompliance of the study lens wear schedule.

3. Total Dispensed: Randomized subjects who administered the test article at least once (i.e. lens insertion occurred in at least one eye).
4. Enrolled Not Dispensed: Subjects who were (i) enrolled in the study (provided informed consent) but failed to satisfy the eligibility criteria (inclusion/exclusion criteria), (ii) randomized but discontinued or drop out prior to administering the test article, or (iii) not randomized to treatment for any reason.
5. Total enrolled (i.e. completed + discontinued + Enrolled not dispensed).

Subjects will be allocated to the following study populations. Safety variables will be summarized on the safety population whereas efficacy variables will be summarized on both the analysis and safety population.

1. Safety Population: All subjects who are administered the test article and have at least one observation on any safety or/and efficacy variables.
2. Analysis Population: All subjects who have successfully completed all required visits without any protocol deviations that the study responsible clinician documents as impacting the assessment of the hypotheses.

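### At Visits 2 and 3 the damaged-lens step has the subject insert the replacement study lens, against the masking rule in Section 4.5

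*Combined protocol and SAP*

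**What the plan says.** Section 4.5 describes a subject-masked study: "Study participants will be masked with respect to the sequence of study lens wear to which they have been assigned". It also gives the means of masking: "An unmasked investigator will insert and remove the study lenses so that the subject is not aware of the study lens type". The rule states its purpose and makes no exception for replacement lenses.

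In the Section 4.7.1 tables, the lens type is taken from the randomisation scheme at step 6 of Visits 2 and 3. Step 7 then tells staff: "Place the lenses on the subject eyes". This agrees with Section 4.5. Step 8, Lens Damage, has the lenses inspected on the eye and continues: "if damaged, record the damage and have the subject insert a new lens". The same instruction stands at Visit 1, step 16, where fitting lenses are worn before randomisation.

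The synopsis describes the Test articles as "hydrogel contact lenses with 1mm wide black annulus and 6mm inner diameter" and says that the Control has the identical design, "except that the test lens has the black annular ring".

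Two later provisions bear on what follows if masking is lost. Section 4.10 says: "Subjects who have had their lens assignment unmasked are expected to return for all remaining scheduled evaluations". Section 9.7 limits the analysis population to completers "without any protocol deviations that the study responsible clinician documents as impacting the assessment of the hypotheses".

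**The concern.** Two operative instructions name different people to insert a randomised lens, and the one in the visit table undoes the masking that the other exists to protect. A 1 mm black ring can be seen on a lens held in the hand.

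Step 8 comes before the visual fields (step 12) and before the time-controlled visual acuity (TCVA), driving and reaction-time assessments (step 13) of the same visit. All of these depend on the subject's responses. The study asks whether the ring harms vision (Section 3.1), so a subject's expectation about the ring bears directly on the question. Masking of the examiner for the primary and secondary endpoints is untouched, but it gives no protection to the driving and reaction-time ratings, which are the subject's own.

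Because there are only two lenses in a cross-over, an event at Visit 2 can also reveal the lens to be worn at Visit 3. An event at Visit 3 affects that visit only.

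**Working it through.** **The texts side by side**

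| Place | Lens in use | Who inserts it |
|---|---|---|
| Section 4.5 | Study lens | Unmasked investigator |
| 4.7.1, Visits 2 and 3, step 7 | Study lens | Placed on the eyes by staff |
| 4.7.1, Visits 2 and 3, step 8 | Replacement study lens | Subject |
| 4.7.1, Visit 1, step 16 | Replacement fitting lens | Subject |

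Only step 8 of Visits 2 and 3 conflicts with Section 4.5. The Visit 1 instruction is harmless: it precedes randomisation, and Section 2.1 mentions the annulus for the Test lens alone. Since the wording is the same, step 8 was probably carried over from Visit 1, but that is an inference.

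**What handling reveals.** A replacement Test lens shows the ring. A clear Control lens is informative only to a subject who knows that the other lens has a ring, and the available text does not establish that. The Test-lens counts below are therefore the more relevant ones.

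**How many subjects.** The plan gives no figure to reproduce. Inputs from the documents: 20 completing subjects (Section 9.2); bilateral wear, so 2 study lenses per visit and 4 per subject; 1:1 allocation, so about 10 subjects wear Test first. Assumptions: damage probability p of 0.01 to 0.05 per lens, independent between lenses; a replacement on hand at the visit; and the site following step 8.

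Expected number of subjects with at least one damaged lens = n × (1 − (1 − p)^k), where k is the number of lenses at risk.

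| Event | n | k | p = 0.01 | p = 0.05 |
|---|---|---|---|---|
| Any study lens, either visit | 20 | 4 | 20 × (1 − 0.99^4) = 0.79 | 20 × (1 − 0.95^4) = 3.71 |
| Any study lens, Visit 2 | 20 | 2 | 20 × (1 − 0.99^2) = 0.40 | 20 × (1 − 0.95^2) = 1.95 |
| Test lens, either visit | 20 | 2 | 0.40 | 1.95 |
| Test lens, Visit 2 | 10 | 2 | 10 × (1 − 0.99^2) = 0.20 | 10 × (1 − 0.95^2) = 0.98 |

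**Effect on the primary comparison.** With 20 complete subjects, 10 per sequence, each subject carries 1/20 of the Test minus Control difference. If unmasking moved one subject's difference by an assumed 1 VA unit, the mean would move by 1/20 = 0.05, which is 0.05/0.5 = 10% of the primary margin. At the upper end of the Test-lens count, with all shifts in the same direction, the movement would be 1.95 × 0.05 ≈ 0.10, about 20% of the margin. The documents do not indicate the direction of any shift.

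**Whether other provisions contain the problem.** Section 4.10 keeps unmasked subjects in the study. Sections 9.1 and 9.7 allow exclusion, but only for a protocol deviation judged to affect the hypotheses. A site that followed step 8 has done what the visit table told it to do, so the event may never be logged as a deviation. Exclusion is uncertain.

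**The case against.** The strongest case on the other side concerns weight, since the conflict in wording is not in dispute. Section 4.5 is the dedicated masking section, is categorical and gives its reason; a site that lets it govern would have no exposure. Harm needs a damaged study lens and a site that follows step 8 instead. The study is a pilot with exploratory hypotheses, the endpoint examiner remains masked, and the self-ratings carry no formal hypothesis. The damage rate and the 1 VA unit shift have no source in the documents, and the shift is twice the primary margin within one subject. The lenses are custom-ordered, and nothing says spares will be at hand. Inserting the lens against Section 4.5 could itself be logged as a deviation. Finally, the step does not say who removes the damaged lens.

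Much of this stands as a limit on size. The counts are upper bounds under stated assumptions, and those that include Control lenses overstate what subjects learn. It does not remove the contradiction. Staff work through the visit table step by step, and the table gives an explicit instruction that defeats the masking method. Replacement is clearly foreseen: reasons for unplanned lens replacement are a listed observation in Section 4.1, and Appendix A provides a form for the replacement lens. Removal needs no new wording, because Section 4.5 already assigns it to the unmasked investigator and step 8 does not say otherwise.

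**Conclusion.** The concern holds. Step 8 of Visits 2 and 3 contradicts Section 4.5, and following it as written would let a subject see the feature under test before that visit's outcomes are measured. This is certain from the text and rests on no assumption.

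The numerical consequence is conditional and probably small: about 0.4 to 2.0 subjects handling a Test lens, of whom about 0.2 to 1.0 at Visit 2, if damage runs at 1% to 5% per lens and sites follow step 8. Each such subject would shift the primary mean by 0.05 per assumed VA unit of change. This does not threaten the validity of the trial. It should still be corrected, because it is a defect in the masking procedure that costs almost nothing to remove.

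**What to change.** In step 8 of Visits 2 and 3, replace the instruction that the subject inserts the new lens with one that the unmasked investigator inserts it, in line with Section 4.5. Leave Visit 1, step 16 as it is. Add one recorded item: any subject who nevertheless handled a study lens is noted as potentially unmasked, with the visit at which it happened. The review of deviations under Sections 9.1 and 9.7 then has the information it needs.

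The cost is wording in two table rows and one data item. Section 4.10 confirms that an unmasked investigator is already at the site, so no staff are added, and the randomisation list does not change.
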